#### **5.3.2.1.5. Thresholds based on HBsAg, HBeAg, HBV DNA and Multiple Markers**

The proportion of participants achieving the cut-offs as defined in Section [5.3.1.1.7](#) will be summarized by cohort and analysis phase over time.

Cumulative percentage of participants achieving any given decrease from baseline in HBsAg, HBeAg and HBV DNA respectively at the end of induction, end of consolidation, and all FU time points, separately, will be presented graphically.

For the thresholds based on multiple markers, the number and proportion of participants who meet the blood marker reduction/seroclearance thresholds at all FU time points, respectively, after stopping all study interventions (including NA) and not having NA re-treated will be summarized descriptively by cohort for each marker and each threshold listed in Section [5.3.1.1.7](#).

#### **5.3.2.1.6. Virologic Breakthrough**

The number and proportion of participants who experience a virologic breakthrough will be summarized descriptively by cohort and analysis phase.

The number and proportion of participants who experience a virologic breakthrough followed by on-treatment biochemical flare will be summarized descriptively by cohort.

#### **5.3.2.1.7. Flares**

The incidence rate will be calculated and summarized for each type of on-treatment or off-treatment flares (virologic, biochemical and clinical) separately, as well as the overall incidence of participants experiencing at least one flare, regardless of type, by cohort. Additionally, for each participant the total number of flares the participant experienced will be counted by type. Such counts will be used to summarize the distribution of the total number of flares by type and by cohort.

For on-treatment biochemical flares, the incidence of flares causing treatment discontinuation will be summarized by cohort. Further, for off-treatment flares, the count and percentage of participants

who experienced a flare followed by NA re-treatment will be summarized by flare type and cohort. Similarly, the incidence of flares followed by the achievement of HBsAg seroclearance (at any time) will be summarized by flare type and cohort.

Flares that are associated with signs of liver decompensation will be provided in a listing.

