### Amendment 4:

Overall rationale of this Amendment:

This administrative amendment incorporates additional clarifications on subgroups and analyses which have been documented in the Data Presentation Specification.

Clarifications, Additions, Corrections		
Section Number and Name	Description of Change	Rationale
2.5.1 Subgroup for Efficacy Analyses	
Addition of the following subgroups:
 
 
- Immune tolerant
 
- Peg-responder definition #1
 
- Peg-responder definition #2
 
 
Removal of the following subgroups:
 
 
- NA treatment history
 
- Fibrosis stage
 
- Sex
 
- Geographical region
 
- Duration of exposure to antigens
 
 
Regrouping of the age categories: >30 years - ≤45 years, >45 years - ≤55 years in one category: >30 years
	To allow for a more focused assessment of factors impacting efficacy outcomes and reduce the overall number of outputs
5.4.1.3.1. Association Between Baseline Characteristics/Viral Blood Markers and Selected Efficacy Variables	Removal of the correlation analyses between off-treatment HBV markers and other endpoints	Insufficient data for correlation analysis since there is only one patient who has met the NA treatment completion criteria and stopped NA (i.e. off-treatment) at CW12.
5.4.1.3.1. Association between several endpoints	The title has been changed to reflect the analyses detailed in this subsection.	To characterize association between changes in viral and safety markers during PegIFN administration.

Clarifications, Additions, Corrections		
Section Number and Name	Description of Change	Rationale

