### 5.3.1.1.9. Flares

The criteria based on blood markers/lab tests for each of the flare types are defined as below.

a) **Virologic flare** is defined as follows:

Virologic flare will be assessed only for those participants who are off-treatment and had HBV DNA  $<$  LLOQ at the last observed time point on all study treatments.

The start of a confirmed virologic flare is defined as the first date of two consecutive visits with HBV DNA  $> 200$  IU/mL. The end date of the same confirmed virologic flare is defined as the first date when HBV DNA value returns to  $\leq 200$  IU/mL or the date of NA treatment restart, whichever comes first. Each virologic flare will be categorized based on the confirmed (i.e., two consecutive values) peak HBV DNA above any of the three thresholds within the start and end date of that flare as follows: 20,000 IU/mL 2,000 IU/mL and 200 IU/mL

- 1 (Yes) = confirmed\*\* HBV DNA  $>$  peak threshold.
- 0 (No) = at least one off-treatment HBV DNA measurement available and not meeting the criteria of confirmed HBV DNA  $>$  peak threshold.
- 2 (Not applicable) = no off-treatment HBV DNA quantitative measurements available.

b) **Off-treatment Biochemical flare** is defined as follows:

The start date of a confirmed off-treatment biochemical flare is defined as the first date of two consecutive visits with ALT and/or AST  $\geq 3x$  ULN and  $\geq 3x$  nadir (i.e., lowest value observed up to the time point of meeting the biochemical flare criteria) while the participant does not receive any of the study interventions. The end date of the same off-treatment biochemical flare is defined as the first date when there is a 50% reduction from the peak ALT and/or AST level &  $< 3x$  ULN.

- 1 (Yes) = confirmed\*\* ALT and/or AST  $\geq 3x$  ULN and  $\geq 3x$  nadir (i.e., lowest value observed during off-treatment period up to the time point of meeting the biochemical flare criteria)
- 0 (No) = otherwise

c) **On-treatment Biochemical flare** is defined as follows:

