The start date of a confirmed on-treatment biochemical flare is defined as the first date of two consecutive visits with ALT and/or AST  $\geq 3x$  ULN and  $\geq 3x$  nadir (i.e., lowest value observed up to the time point of meeting the biochemical flare criteria) while the participant receives any of the study interventions. The end date of the same on-treatment biochemical flare is defined as the first date when there is a 50% reduction from the peak ALT and/or AST level &  $< 3x$  ULN, regardless of stopping the study interventions.

- 1 (Yes) = confirmed\*\* ALT and/or AST  $\geq 3x$  ULN and  $\geq 3x$  nadir (i.e., lowest value observed on-treatment period up to the time point of meeting the biochemical flare criteria)
- 0 (No) = otherwise

d) **Clinical flare** is defined as follows:

A clinical flare occurs either when a virologic flare and biochemical flare overlap in time or when a biochemical flare starts within 4 weeks following the end of a virologic flare. The start date of a clinical flare is defined as the minimum start date of the virologic flare and the biochemical flare. The end date of a clinical flare is defined as the maximum end date of the virologic flare and biochemical flare, i.e., the later date between HBV DNA returns to  $\leq 200$  IU/mL and 50% reduction from the peak ALT and/or AST level &  $< 3x$  ULN .

- 1 (Yes)= confirmed\*\* HBV DNA  $>$  peak threshold and confirmed\*\* ALT and/or AST  $\geq 3x$  ULN and confirmed\*\*  $\geq 3x$  nadir (i.e., lowest value observed during off-treatment period up to the time point of meeting the flare criteria).
- 0 (No) = otherwise

\*\* Confirmed means that the criterion should be fulfilled at 2 or more consecutive time points or at the last observed time point.

The virologic and clinical flares will be assessed only off-treatment, while biochemical flares will be identified on treatment and off treatment, respectively. On-treatment virologic flares are described as virologic breakthrough in Section 5.3.1.1.8. On-treatment will be defined as the time period in which the participant receives any of the study interventions. Off-treatment will be defined as the period after stopping all study interventions (including NA). In addition, the proportion of subjects with off-treatment virologic flares, ALT and clinical flare for subjects who met NA treatment completion criteria and stopped NA will be shown.

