### **5.3.2. Analysis Methods**

Statistical analyses of all secondary endpoints will be performed by cohort using Treated analysis set. The selected secondary endpoints efficacy analyses will use combining the data from participants who received PegIFN- $\alpha$ 2a but not JNJ-6379 in Cohort 1 with data of Cohort 2, the PegIFN- $\alpha$ 2a ITT analysis set will be used. If applicable, additional statistical analyses (descriptive statistics and spaghetti plots) may be added for each of the following subgroups: participants who

received at least one dose of JNJ-6379 and an induction phase duration of  $\leq 36$  weeks, participants who received at least one dose of JNJ-6379 and an induction phase duration  $> 36$  weeks, participants who never received JNJ-6379. The mTreated and mPegIFN- $\alpha$ 2a ITT will be used if relevant difference between the sets exists (see Section 2.3).

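### Off-treatment biochemical and clinical flares have no 'Not applicable' code, so participants who never stopped NA enter the SAP 5.3.2.1.7 denominators as non-events

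*SAP*

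**What the plan says.** SAP 5.3.1.1.9 defines four kinds of flare.

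- **(a) Virologic.** The population is restricted: "Virologic flare will be assessed only for those participants who are off-treatment and had HBV DNA" below LLOQ at the last time point on all study treatments. The flag has three levels, the third being "2 (Not applicable) = no off-treatment HBV DNA quantitative measurements available".
- **(b) Off-treatment biochemical.** The flag is Yes or "0 (No) = otherwise". There is no third level.
- **(c) On-treatment biochemical.** Yes or No.
- **(d) Clinical.** A virologic and a biochemical flare must overlap, or the biochemical flare must start within 4 weeks of the end of the virologic one. The flag again has only Yes and 'No = otherwise'.

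The same section adds that "The virologic and clinical flares will be assessed only off-treatment", and it defines off-treatment as the period after everything, NA included, has been stopped. It closes with a supplementary summary: the proportions with off-treatment virologic, ALT and clinical flares among subjects who met the NA completion criteria and stopped NA.

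For the analysis, SAP 5.3.2.1.7 states: "The incidence rate will be calculated and summarized for each type of on-treatment or off-treatment flares (virologic, biochemical and clinical) separately". It also plans the distribution of the number of flares per participant, by type and cohort. It gives no denominator. The general rule is in SAP 5.3.2: "Statistical analyses of all secondary endpoints will be performed by cohort using Treated analysis set".

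Under SAP 1.2 and Protocol 6.6.1, a participant who misses the NA completion criteria at consolidation Week 12 continues NA through follow-up. SAP Amendment 4 records that "there is only one patient who has met the NA treatment completion criteria and stopped NA (i.e. off-treatment) at CW12".

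**The concern.** An off-treatment flare can be observed only in someone who has an off-treatment period. A participant on NA for the whole of follow-up has none. The virologic definition recognises this; definitions (b) and (d) do not, and 'otherwise' sweeps that participant into 'No'. With the Treated set as denominator, the off-treatment biochemical and clinical incidences then depend as much on how few people stopped NA as on what happened to those who did.

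The codes also conflict. A clinical flare cannot exist without a virologic flare, yet one participant can be 'Not applicable' for the component and 'No' for the composite.

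This matters because flare frequency is listed among the follow-up secondary endpoints, and Protocol 2.3.2.2 names hepatitis B flares as a risk of discontinuing NA. A low percentage in the main table could be read as reassurance about stopping NA when it mostly reflects continued NA.

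**Working it through.** **1. How the flags fall for a participant who stays on NA through follow-up**

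| Flare type | Flag under 5.3.1.1.9 | Off-treatment event possible? |
|---|---|---|
| (a) Virologic | Not assessed / 2 (Not applicable) | No |
| (b) Off-treatment biochemical | 0 (No) | No |
| (d) Clinical | 0 (No) | No, since it needs (a) |

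**2. Is the missing restriction a deliberate choice?** Neighbouring sections restrict where the event depends on stopping NA. SAP 5.3.2.1.1.2 limits the re-treatment analysis to ITT participants who met the criteria and actually stopped NA. SAP 5.3.2.1.2 and 5.3.2.1.4 add summaries restricted to those who stopped all interventions and had not restarted NA. Section 5.3.2.1.7 has no such sentence, which points to an omission.

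**3. Formula.** Let N be the treated number, m the number ever off treatment, and x the number with an off-treatment flare.

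- Reported: x/N. Among those at risk: x/m.
- x/N = (x/m) × (m/N), so the dilution factor is N/m.

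**4. Inputs.** The flare sections contain no figure to reproduce. The planning numbers (SAP 1.4) do reproduce: 33 × 0.9 = 29.7, about 30, and the Clopper-Pearson 90% interval for 15/30 is 0.339 to 0.661, as stated. I use planned N = 33 (Cohort 2) and N = 60 (total) because the treated N is not given. Amendment 4 gives one participant who met the criteria and stopped NA; m = 1 is therefore an illustration, not a known value.

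**5. Illustration with m = 1 (Clopper-Pearson 90% intervals)**

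| Denominator | x = 1 | x = 0: upper limit |
|---|---|---|
| Planned Cohort 2 | 1/33 = 3.0% (0.2 to 13.6%) | 8.7% |
| Planned total | 1/60 = 1.7% (0.1 to 7.7%) | 4.9% |
| At risk | 1/1 = 100% (5 to 100%) | 95% |

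The cohort of that participant is not stated. If it is Cohort 1, with 60 − 33 = 27 by subtraction, one flare would read 1/27 = 3.7%.

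**6. Sensitivity of N/m**

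- m = 3 (assumption): 33/3 = 11 to 60/3 = 20.
- 19.1% stopping NA (the NA-completion rate that Protocol Appendix 14, Amendment 5, quotes from REEF-1 for the 200 mg dose): 1/0.191 = 5.2.
- 50% stopping NA (assumption): 1/0.5 = 2.

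**7. What the supplementary summary reaches.** It covers participants who met the criteria and stopped NA. It does not change flags (b) and (d), the by-cohort incidence, or the flare-count distribution. Nor does it cover anyone off all interventions without meeting the criteria. Protocol 7.1 allows NA to be discontinued on investigator judgement in consultation with the sponsor, and the note in Protocol 6.6.1 allows NA completion to be considered after an ALT elevation. The documents do not say how many such participants there were.

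**The case against.** The strongest reply has five parts.

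- **The at-risk proportion is already planned.** True for those who met the criteria and stopped NA, for all three off-treatment types. A reader might infer that only a diluted figure will be reported; the documents do not support that.
- **The denominator is inferred.** Also true. Section 5.3.2.1.7 names none, and 'otherwise' could be read as 'otherwise among those assessed'. Nor does the SAP say how code 2 enters the virologic denominator. But the only stated rule is the Treated set, and text that allows two readings of a safety percentage needs settling.
- **A proportion of all treated participants is a legitimate quantity.** It describes the whole strategy, including its NA-stopping rule, and Protocol 9.4.1.2 does speak of the proportion of participants with flares by cohort. So 'bias' is too strong a word. That reading still does not explain why virologic flare is handled differently, or why its composite is coded 'No' when it is 'Not applicable'.
- **A 33- to 60-fold dilution is not established.** Correct. It rests on planned N and on a count that may leave out participants who stopped NA by another route.
- **The safety signal is not lost.** ALT flares on continued NA count as on-treatment biochemical flares, the independent panel adjudicates flares, flares with signs of decompensation are listed, and no test or decision rule uses the incidence.

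These points limit the size and consequence. They do not remove the coding gap.

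**Conclusion.** The point holds as a coding and denominator defect in the off-treatment biochemical and clinical flare outputs of SAP 5.3.2.1.7: the by-cohort incidence and the flare-count distribution. As written, and with the Treated-set default, both include participants who could not have the event, and the clinical flag can contradict the virologic one. The dilution factor is the treated N divided by the number ever off treatment. Its direction is certain whenever some participants never stop NA; its size is not. The figures of 1/33 and 1/60 against 1/1 illustrate it on planned numbers and one known participant.

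Two stronger readings should be resisted. First, flare incidence as a whole is not diluted: virologic flare is restricted to off-treatment participants, on-treatment flares can occur in any treated participant, and the incidence of at least one flare of whatever type properly uses all treated. Second, correcting the denominator will not yield an informative rate. With one participant at risk, 1/1 has a 90% interval of 5 to 100%. The gain is that the table shows how little off-treatment information there is.

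**What to change.** In SAP 5.3.1.1.9:

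- add to (b): '2 (Not applicable) = no off-treatment ALT/AST measurement available';
- add to (d): '2 (Not applicable) = not evaluable for off-treatment virologic or biochemical flare'.

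In SAP 5.3.2.1.7, state that each off-treatment incidence and each off-treatment flare-count distribution uses evaluable participants with at least one off-treatment measurement of the marker concerned, and print that N beside every percentage. Keep all treated participants as the denominator for on-treatment flares and for the any-type incidence. The supplementary summary in 5.3.1.1.9 can stay as it is.

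The cost is two code values and one denominator sentence, following the rule the SAP already applies to virologic flare. No new data are needed. The drawback is that the off-treatment percentages will rest on very few participants, perhaps one, and may look less favourable; the printed N makes that visible.

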### **5.3.2.2. Values and Change Over Time Endpoints**

#### **5.3.2.2.1. HBsAg, HBeAg, HBV DNA and ALT**

Descriptive statistics on actual values (original unit and  $\log_{10}$  transformed values), changes from baseline ( $\log_{10}$  transformed values), changes from consolidation reference time point ( $\log_{10}$  transformed values) over time in HBsAg, HBeAg, HBV DNA and ALT will be summarized by cohort and analysis phase. Mean (+/- SE) plots of the actual values, change from baseline ( $\log_{10}$  transformed) and change from consolidation reference time point ( $\log_{10}$  transformed) will be presented over time per blood marker by cohort and analysis phase.

In addition, the change from baseline value to the nadirs (i.e., maximum decrease for each participant) will be summarized descriptively by cohort. Box plots of the changes to nadir in HBsAg, HBeAg and HBV DNA will display the distribution by cohort.

Descriptive statistics on actual values (original unit and  $\log_{10}$  transformed values) and changes from baseline ( $\log_{10}$  transformed values) at end of consolidation in HBsAg, HBeAg, HBV DNA and ALT (original unit), respectively, will be summarized by cohort, by NA treatment completion criteria status at the end of consolidation phase, by functional cure status at FU Week 24 and 48, and for participants who achieved functional cure 24 weeks after stopping all study interventions regardless of meeting the NA completion criteria) and at the end of FU phase.

Cross-tabulations overtime and overall of quantitative versus qualitative HBsAg and HBeAg values, respectively, will also be presented.

Spaghetti plots for both absolute values and changes from baseline of HBsAg, HBeAg, HBV DNA and ALT will be presented over time (all data collected including unscheduled visit, all data within the same time interval, see [Section 2.1.3](#)) per blood marker by cohort and by selected subgroups (e.g. HBV Genotype), by NA treatment completion criteria status at the end of consolidation phase, by functional cure status at FU Week 24 and 48, and for participants who achieved functional cure 24 weeks after stopping all study interventions regardless of meeting the NA completion criteria) and at the end of FU, separately, will be presented graphically.

Shift tables in HBV DNA categories from baseline will also be summarized by cohort and analysis phase.

### **5.3.2.3. Time to Event Endpoints**

All time to event variables will be analyzed for all treated participants.

### 5.3.2.3.1. Time to First HBsAg Seroconversion

Time to first HBsAg seroconversion will be summarized. The Kaplan-Meier method will be used to estimate and plot the cumulative incidence. The median time with 90% CI will be estimated using Kaplan-Meier method.

In addition, the number and percentage of participants who had an event or were censored will be reported.

### 5.3.2.3.2. Time to First HBV DNA < LLOQ

Time to HBV DNA < LLOQ will be analyzed following the methodology in Section [5.3.2.3.1](#).

## 5.4. Exploratory Endpoints

### 5.4.1. Definitions

#### 5.4.1.1. Binary and Categorical Endpoints

##### 5.4.1.1.1. End of Follow-up Phase HBsAg response

The number and proportion of participants with sustained response according to the below different definitions will be summarized descriptively by cohort, combined cohort, overall and by analysis phase.

End of follow-up phase HBsAg Response definition #1:

- For participants with Follow-up Week 48 data: participants who had a  $>1 \log_{10}$  decline from baseline in HBsAg at Follow-up Week 48 and HBsAg < 1000 IU/mL at Follow-up Week 48
- For participants without Follow-up Week 48 data: participants who had a  $>2 \log_{10}$  decline from baseline in HBsAg at Follow-up Week 24 or a  $>1.5 \log_{10}$  decline from baseline in HBsAg at Follow-up Week 36 (most recent value used) and HBsAg < 1000 IU/mL at the last available timepoint.

End of follow-up phase HBsAg Response definition #2:

- For participants who had a  $>1 \log_{10}$  decline from baseline in HBsAg at the last Follow-up visit: among the 3 most recent visits, the difference between  $\log_{10}$  HBsAg at 2 of the 3 last visits and 1 of the 3 last visits is  $< 0.2$ , and the difference between  $\log_{10}$  HBsAg at 3 of the 3 last visits and 1 of the 3 last visits is  $< 0.2$ .

End of follow-up phase HBsAg Response definition #3:

- For participants with a  $>1 \log_{10}$  decline from baseline in HBsAg at the last Follow-up visit: among the 3 most recent visits, the difference between  $\log_{10}$  HBsAg at 2 of the 3

last visits and 1 of the 3 last visits is  $<0.2$ , and the difference between  $\log_{10}$  HBsAg at 3 of the 3 last visits and 1 of the 3 last visits is  $<0.2$  and had HBsAg  $<1,000$  IU/mL at the last available timepoint.

End of follow-up phase HBsAg Response definition #4:

- Three categories regarding the difference between HBsAg level at the last Follow-up timepoint from CW12:
  - $>0.2 \log_{10}$  decrease: Decreasing level
  - $\leq 0.2 \log_{10}$  increase or  $\leq 0.2 \log_{10}$  decrease: Stable level
  - $>0.2 \log_{10}$  increase: Increasing level

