- a. All follow up study visits are to be scheduled relative to the last dose of JNJ 3989/PegIFN α2a. An unscheduled visit can be performed upon the investigator's discretion, in case of HBV DNA elevations, ALT elevations, other signs of worsening of liver disease, or for any other reason during follow up.
- Participants who withdraw consent during follow up will be offered an optional safety follow up visit.
- c. Participants who discontinue study intervention early will have an early WD visit and will enter follow up unless they withdraw consent. Participants who withdraw consent during study intervention will be offered an optional safety follow up visit to occur on the day of consent withdrawal. For the optional safety follow up visit, assessments are at the investigator's discretion and could be similar to the early WD visit.
- d. Follow up Week 8, 16, 20, 28, 32, 40, and 44 visits are not required for participants who did not complete NA treatment at Follow up Week 2 and for participants who have restarted NA treatment during the follow up period, provided that their HBV DNA and ALT values are stable.
- e. In between study visits, participants will take NA orally at home and will bring their NA with them to each study visit. At study visits, NA should be taken on site. PegIFN α2a should be administered weekly, preferably in the evening by self injection. If desired, participants can also choose to have the weekly administration of PegIFN α2a performed on site irrespective of the time of day. PegIFN α2a should preferably be administered in the evening prior to the sparse PK visit, or alternatively in the morning of the visit on site.

- f. No JNJ 3989/PegIFN α2a will be administered or dispensed during follow up. Administration/Dispensation of NA is only applicable for participants who could not stop NA treatment, or for those who met the NA re treatment criteria. In between study visits, participants will take NA at home and they will bring their NA treatment with them to each study visits, the NA treatment should be taken on site.
- g. If the NA treatment completion criteria are met at consolidation Week 12, treatment with NA will be completed at FU Week 2.
- h. Complete physical examination, including body weight, skin examination, and other body systems.
- i. Vital signs include supine SBP, DBP, pulse rate, and body temperature.

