# 4.3.1. JNJ-3989

Clinical data on PK, efficacy, and safety of JNJ-3989 are available from the ongoing Phase 1/2a AROHBV1001 study with a data cut-off date of 29 October 2019. All dosing with JNJ-3989 has been completed and ongoing participants are in the follow-up phase. Twenty adult healthy participants have received single subcutaneous injections of JNJ-3989 (35, 100, 200, 300, and 400 mg) and 84 adult chronic HBV-infected participants have received multiple doses of JNJ-3989 (25, 50, 100, 200, 300, and 400 mg), administered as 3 subcutaneous injections separated by either 7-day, 14-day, or 28-day intervals. All participants either continued or started on ETV or tenofovir disoproxil on Day 1.

JNJ-3989 was generally safe and well tolerated at all doses. No clinically relevant safety signal was identified.

Antiviral activity data were available for 56 chronic HBV-infected participants who received 3 subcutaneous injections of 25 to 400 mg JNJ-3989 Q4W. In general, mean HBsAg declines reached nadir at Day 113 (ie, 8 weeks after last JNJ-3989). Mean HBsAg levels remained suppressed (below baseline levels) at least until Day 392 (ie, 9 months after last dose) in a substantial proportion of patients. The HBsAg levels at Day 392 were variable with some patients having HBsAg levels close to baseline levels while a substantial proportion of patients still had HBsAg levels >1 log10 IU/mL lower than the baseline levels. JNJ-3989 showed activity on other serological markers (HBV DNA, HBV RNA, HBeAg and HBcrAg), frequently with sustained reduction at least until day 362. No apparent dose response was observed at doses between 100 mg and 400 mg JNJ-3989, a numerically smaller mean decline was observed at the lower doses of 25 mg and 50 mg, mainly apparent after end of JNJ-3989 dosing.

A dose of 200 mg JNJ-3989 Q4W is chosen based on the observed decline in HBsAg in Study AROHBV1001 at this dose over 3 injections, and the lack of a substantial incremental efficacy response at higher doses.

The Phase 2b study REEF-1 is designed to establish the optimal dose of JNJ-3989. Based on data from the Phase 1/2a study AROHBV1001 with limited treatment duration, 200 mg was selected

as the highest dose of JNJ-3989 tested in REEF-1. Until lower doses are proven equivalently effective in REEF-1, additional combination studies with JNJ-3989 and JNJ-6379 are conducted with 200 mg of JNJ-3989.

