**c) Follow-Up Phase (Cohort 1 & 2)**

Analysis phase (FU)	Target day	Analysis time point (Week)			Analysis time point (label)	Time interval (FU days) n
Follow-up	15	ATEOC o +1	50	50	FU Week 2	[1, 22]
	29	ATEOC o +3	52	52	FU Week 4	[23, 43]
	57	ATEOC o +7	56	56	FU Week 8	[44, 71]
	85	ATEOC o [contact]	FU Week 12	[72, 99]
	113	ATEOC o [contact]	FU Week 16	[100, 127]
	141	ATEOC o [contact]	FU Week 20	[128, 155]
	169	ATEOC o [contact]	FU Week 24	[156, 183]
	197	ATEOC o [contact]	FU Week 28	[184, 211]
	225	ATEOC o [contact]	FU Week 32	[212, 239]
	253	ATEOC o [contact]	FU Week 36	[240, 267]
	281	ATEOC o [contact]	FU Week 40	[268, 295]
	309	ATEOC o [contact]	FU Week 44	[296, 323]
	337	ATEOC o [contact]	FU Week 48	[324, + $\infty$ ]
	last visit in the study	999 k,p	999 l,p	999 m,p	EOS p	

k Analysis time point for Cohort 1 will be based on end date of the induction and consolidation phase.

l Analysis time point for Cohort 1 will be based on end date of the induction and consolidation phase.

m Analysis time point for Cohort 2 will be based on end date of the induction and consolidation phase.

n Relative to follow-up start date.

o ATEOC = Analysis time point (Week) for EOC.

p End of study (EOS) visit (last available data during the follow-up) will be the last visit in the study.

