## 5.4.2. Analysis Methods

Statistical analyses of all exploratory endpoints will use descriptive statistics. Treated analysis set will be used. The selected exploratory endpoints efficacy analyses will use combining the data from participants who received PegIFN- $\alpha$ 2a but not JNJ-6379 in Cohort 1 with data of Cohort 2, the PegIFN- $\alpha$ 2a ITT analysis set will be used. If applicable, additional statistical analyses (descriptive statistics and spaghetti plots) may be added for each of the following subgroups: participants who received at least one dose of JNJ-6379 and an induction phase duration  $\leq$ 36 weeks, participants who received at least one dose of JNJ-6379 and an induction phase duration  $>$ 36 weeks, participants who never received JNJ-6379. The mTreated and mPegIFN- $\alpha$ 2a ITT will be used if relevant difference between the sets exists (see Section 2.3).

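### Two of the sustained HBsAg response definitions (#2 and #3) set no minimum follow-up, so an early leaver can count as a sustained responder; trend category #4 shares the gap

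*SAP*

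**What the plan says.** SAP 5.4.1.1.1 introduces all four definitions under one label: "The number and proportion of participants with sustained response according to the below different definitions" are to be summarised.

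- **Definition #1** is tied to FU Week 48 (decline above 1 log10 and HBsAg below 1,000 IU/mL). It has a separate branch that begins "For participants without Follow-up Week 48 data: participants who had a" and asks for a larger decline: above 2 log10 at FU Week 24, or above 1.5 log10 at FU Week 36.
- **Definitions #2 and #3** need more than a 1 log10 "decline from baseline in HBsAg at the last Follow-up visit: among the 3 most recent visits, the difference between" log10 values must be under 0.2. Definition #3 adds HBsAg below 1,000 IU/mL.
- **Definition #4** forms "Three categories regarding the difference between HBsAg level at the last Follow-up timepoint from CW12": decreasing, stable or increasing, with 0.2 log10 as the limit.

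The only definition of a last visit is in SAP Table 2c: "End of study (EOS) visit (last available data during the follow-up) will be the last visit in the study". For exploratory endpoints, SAP 5.4.2 states that "Treated analysis set will be used". Visit frequency depends on nucleos(t)ide analogue (NA) status. Protocol 1.3.2, footnote d, says that "Follow up Week 8, 16, 20, 28, 32, 40, and 44 visits are not required for participants who did not complete NA treatment" at FU Week 2. The same relief covers those who restarted NA, with a proviso that HBV DNA and ALT are stable.

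**The concern.** A sustained response should mean that HBsAg stays low after the drugs have worn off. On carry-over, Protocol 4.3.1 reports for an earlier study that "mean HBsAg declines reached nadir at Day 113 (ie, 8 weeks after last JNJ-3989"), with mean levels still below baseline at Day 392. Three flat values soon after treatment may therefore reflect residual drug effect. Definitions #2 and #3 accept such values from someone who then leaves, because a later rebound is never seen.

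The SAP protects itself against this elsewhere. Definition #1 raises the bar when FU Week 48 is missing, and SAP 5.3.1.1.3 lets a missing FU Week 48 HBsAg be filled only from FU Week 36 onward. With only one participant reported as stopping NA at Consolidation Week 12 (CW12) (SAP Amendment History, Amendment 4), how long the HBsAg reduction lasts is an important remaining follow-up result.

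**Working it through.** **1. The plan's own timing figure.** Three injections every 4 weeks fall on Days 1, 29 and 57. (113 − 57)/7 = 8.0 weeks, which matches Protocol 4.3.1.

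**2. Applied to this trial (an assumption).** The last JNJ-3989 injection is at Consolidation Week 8 (Protocol 1.3.2) and follow-up starts after about Week 12 (SAP Table 1), so FU Week w is about w + 4 weeks after the last injection.
- Nadir: 8 − 4 = about FU Week 4.
- Day 392: (392 − 57) = 335 days = 47.9 weeks, so about FU Week 44. The protocol calls Day 392 9 months after the last dose, but 335/30.4375 = 11.0 months. Using 9 months instead: 9 × 30.4375/7 = 39.1 weeks, so about FU Week 35.
- A leaver at FU Week 12 is 16 weeks after the last injection, inside either period.

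**3. Can an early leaver qualify?** Required visits for those on NA are FU Weeks 2, 4, 12, 24, 36 and 48. A leaver at FU Week 12 has three values, at Weeks 2, 4 and 12.
- Definition #1: not counted, as there is no FU Week 24, 36 or 48 value.
- Definition #2: counted if more than 1 log10 below baseline and flat.
- Definition #3: counted if HBsAg is also below 1,000 IU/mL.
- Definition #4: a category is assigned, possibly from FU Week 2 alone.

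The 1 log10 gate filters little. The other study's on-treatment decline at Week 48 was 3.56 (SD 1.328) log10 (Protocol 10.14, Amendment 5 rationale). Assuming normality, z = (3.56 − 1)/1.328 = 1.93, so about 97% exceed 1 log10 at end of treatment.

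The stability test is also easier early. Take a true linear rebound of 0.01 log10 per week, independent normal assay error and absolute differences (all assumed). The simulated probability of passing is:

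| Assay SD (log10) | FU Weeks 2, 4, 12 | FU Weeks 24, 36, 48 |
|---|---|---|
| 0.03 | 0.99 | 0.17 |
| 0.05 | 0.92 | 0.28 |
| 0.10 | 0.65 | 0.33 |

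**4. Upper bound.** SAP 1.4 assumes 10% dropout, from 33 to 30 in Cohort 2. 33 − 30 = 3, and 3/33 = 9.1 percentage points; each participant is worth 1/33 = 3.0 points.

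**5. Visit spacing (secondary).**

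| Last visit | 4-weekly visits | Span (weeks) | Reduced schedule | Span (weeks) | Ratio |
|---|---|---|---|---|---|
| FU W12 | 4, 8, 12 | 8 | 2, 4, 12 | 10 | 1.25 |
| FU W24 | 16, 20, 24 | 8 | 4, 12, 24 | 20 | 2.5 |
| FU W36 | 28, 32, 36 | 8 | 12, 24, 36 | 24 | 3.0 |
| FU W48 | 40, 44, 48 | 8 | 24, 36, 48 | 24 | 3.0 |

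At FU Week 48 the fastest linear rebound that still passes is 0.2/8 = 0.025 log10 per week on 4-weekly visits and 0.2/24 = 0.0083 on the reduced schedule.

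**The case against.** A reader might infer that three of the four definitions turn early leavers into sustained responders. The text does not support that. Definition #4 has no responder class, no 1 log10 gate and no three-visit test, so only #2 and #3 can do so. Nor do leavers count automatically. They must pass the decline and both 0.2 log10 differences, and for #3 the 1,000 IU/mL limit. Needing three visits is itself an implicit minimum: if these must be follow-up visits, FU Week 8 on 4-weekly visits or FU Week 12 on the required visits.

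The carry-over timing is also borrowed. It is a group mean after three injections, whereas Cohort 2 is planned to receive 9 + 3 = 12 injections (SAP 4.7) plus PegIFN. The earlier study found that many participants stayed more than 1 log10 below baseline at Day 392, so an early leaver scored as sustained is not necessarily misclassified.

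Definition #1 is reported alongside, HBsAg thresholds are tabulated over time and individual profiles are plotted. These are descriptive exploratory endpoints with no formal test.

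All of this limits the size of the point. It does not close the gap. Protocol 9.4.1.2 offers a non-response rule for missing binary data, but it is optional and works from a named time point, which #2 to #4 lack. SAP 5.4.1.1.1 does not invoke it.

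**Conclusion.** The point holds for definitions #2 and #3, and in a weaker form for #4. The missing minimum follow-up is a fact of the text. That early values reflect residual drug effect is an assumption carried over from another study.

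The 9 percentage points are a ceiling, not an expected error. The 10% dropout covers the whole period to the primary endpoint, and participants who withdraw before follow-up have no follow-up visits to score. Reaching the ceiling needs all three losses early in follow-up and all three passing every gate.

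A reader might also infer from the spacing table a threefold difference in the stability test by NA status. The ratio is right for last visits at FU Week 36 or 48, but it has little practical weight. SAP Amendment 4 reports a single participant who stopped NA at CW12, so nearly everyone shares the reduced schedule. The skipped visits are also optional rather than barred, and the ratio for a FU Week 12 leaver is 1.25.

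The primary and secondary endpoints are unaffected.

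**What to change.** In SAP 5.4.1.1.1:

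- **Definitions #2 and #3:** use the FU Week 24, 36 and 48 analysis visits, which are required for every participant, in place of the three most recent visits.
- **FU Week 48 missing, FU Week 36 present:** require definition #1's decline above 1.5 log10 at FU Week 36 and a difference below 0.2 log10 between FU Weeks 24 and 36. For #3, keep the 1,000 IU/mL limit.
- **No HBsAg at FU Week 36 or later:** non-responder for #2 and #3.
- **Definition #4:** compare FU Week 48 with CW12, carry forward nothing earlier than FU Week 36 (as in SAP 5.3.1.1.3), and otherwise report as not evaluable.

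While the text is open, state whether the 0.2 log10 differences are signed or absolute, and what happens when FU Week 48 is present but FU Week 24 or 36 is missing.

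Cost: SAP wording and reprogramming of three exploratory flags, with no new data. Slightly fewer responders may be reported.
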